 - 9. Questionnaires: Symptoms of fatigue, depression, anxiety, and pain will be measured by the Fatigue Severity Scale (FSS), Modified Fatigue Impact Scale (MFIS), Hospital Anxiety and Depression Scale (HADS), and short-form McGill Pain Questionnaire (SF-MPQ) respectively. The FSS is a 9-item unidimensional measure of fatigue and its disabling consequences over the past week in medical populations including MS. The MFIS is a 21-item measure of physical, cognitive, and psychosocial impact of fatigue on daily life over the past 4 weeks. The HADS contains 14 items that measure the frequency of anxiety and depressive symptoms over the past week. The SF-MPQ has a 15-item adjective checklist that captures sensory and affective dimensions of pain experienced over the past week. These variables will be measured at baseline, 8 and 16 weeks.**
 - 10. Dietary adherence: Participants will be asked to will complete three 24 hour dietary phone recalls over a 14 day period. These calls will be unannounced and participants will be informed that they will be asked to recall all they consumed within the last 24 hours at the time of the call. They will receive two of the three recall phone calls during the week, and one on a Monday morning to capture a weekend recall. Research staff will follow standard protocols for performing a 24 hour food recall and study staff will provide participants with materials at baseline to help them answer the food recall questions. Participants will receive three more 24 hour dietary recall phone calls at the 16 week mark.**

At the end of the baseline visit, research staff will give the participant information for accessing the questionnaires on-line. Participants will be given the option to complete the questionnaires while at the visit or at home. Participants will be given an accelerometer to wear for 14 days, along with a pre-stamped envelope and instructions to mail back the accelerometer after the 14 days. Participants will also receive instructions on for completing the 24 hour dietary recall phone calls. All participants will receive a take home folder containing instructions for the two weeks following baseline as well as information for depression in individuals with MS, provided by the National MS Society.

At 14 days after baseline, staff will contact participants to remind them to return their accelerometer via mail, complete any questionnaires that have not been completed, and to schedule their first coaching appointment.

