III. INTERVENTION

The intervention consists of a 16 week internet-based health coaching intervention. All participants (both groups) will interact with the BIAPAMS website weekly, and have one-on-one video chats with a health coach in weeks 1-12, 14, and 16. In addition to the BIPAMS website, participants in the BIPAMS+Diet group will be asked to log their food intake using a mobile app, beginning in week 9. All participants (both groups) will work toward physical activity goals focused on increasing daily steps. In addition to these goals, participants in the BIPAMS+Diet group will be given weekly dietary goals related to intake of various food groups each week, beginning in week 9. All goals are individualized the participant and therefore will be different for each participant.

The intervention consists of 3 components: the BIPAMS website (both groups), HealthWatch 360 mobile/desktop app (BIPAMS+Diet group only), and One-on-One video chats (both groups). All participants will receive the standard BIPAMS intervention for the first 8 weeks of the trial. At the completion of the eighth week, participants will receive their randomization assignment. Those in the BIPAMS+Diet arm will begin receiving dietary materials in week 9. Those in the comparison group (BIPAMS) will continue receiving the established BIPAMS intervention for the remainder of the trial.

We have chosen to structure the intervention in this way for two reasons. First, persons with MS often report symptom burden as reasons for difficulty in establishing new health behaviors. For this reason, initiating multiple behaviors simultaneously may be more difficult for this group than the general population. By initiating physical activity first, we hope to maximize participants' adherence to the recommendations by reducing the potential psychosocial and physical stressors of concurrent behavior changes. Secondly, starting with the portion of the intervention that has already been established as efficacious will allow us to use the first 8 weeks as a run-in period and better differentiate the effects of the combined approach of diet and exercise compared to the exercise-alone intervention.

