real time and monitor the nutrition goals of participants. The research portal is HIPAA-compliant. Upon completion of the study, the participant may continue to use the HealthWatch 360 application as it is free to the public, but the research portal license will expire so the researchers will no longer be able to track the entries and nutrition goals of the participants. If the participant prefers to remove the application from their mobile device, study staff will assist in the deletion of the program from the mobile device per the application deletion procedure for the specific type of mobile device.

3. **One-on-one Video Chats:** The one-on-one video chats support adherence with the intervention, discussion and elaboration of website material, supportive accountability, and reporting adverse events/injuries; these further provide vicarious experience (i.e., social interaction) for promoting behavior change. The video chats are modeled for maximizing adherence with Internet interventions, provide an ongoing interaction between the behavioral coach and the participant, and are conducted face-to-face through the web-based program Zoom™. The video chats are semi-scripted and based on principles of supportive accountability. The video chats consist of an ongoing review of goal-setting and progress toward goal attainment through Tracker as well as discussion of strategies and facilitators of behavioral change based on SCT and current website content. Supportive accountability, for example, is accomplished by encouraging participants to wear the pedometer daily, and monitor behavioral change and goal attainment throughout the 4-month intervention. The chats occur weekly during the first 3 months (12 total calls), and bi-weekly during the last month (2 total calls) of the intervention.

IV. FOLLOW UP DATA COLLECTION

At the half-way point of the intervention (week 8), participants will be asked to wear the accelerometer again for 1 week, and complete the questionnaires online again. Participants will not be asked to come into the lab at this point. Accelerometers will be mailed to them and questionnaires will only be done online.

At completion of the 16-week intervention, participants will be scheduled to return to Lakeshore Foundation. All baseline testing will be repeated following the same protocols as baseline.

- What is the probable length of time required for the entire protocol (i.e., recruitment through data analysis to study closure)? 1 year.

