- ii. What data will be shared? _____
- iii. How will the data be identified, coded, etc.? _____

24. Genomic Data Sharing (GDS)

Researchers who collect genomic data as part of a NIH grant funded after January 25, 2008 may be required to submit those data to a NIH database for broad scientific sharing. See [Genomic Data Sharing](#) in the IRB Guidebook for more information.

- a. Does this protocol involve the proposed submission of genetic data into genomic repositories created to share genetic information for research purposes? Yes No
- b. Will UAB be uploading the final genomic data to the central repository (e.g., dbGaP)? Yes No
- If Yes to both a and b, submit a Detailed Data Sharing Plan to the IRB for review. This plan should include any known data use limitations and indicate whether aggregate-level data are appropriate for general research use. For guidance see the [NIH Genomic Data Sharing Policy](#).
- c. Submit a copy of the NIH Institutional Certification Form.
- To determine which certification form to include, answer i-ii.
- i. Was this protocol funded prior to January 25, 2015? Yes No
- If yes, and consent will be obtained, submit the [Extramural Institutional Certification - Before January 25 - With Consent](#).
 - If yes, and consent will not be obtained, submit the [Extramural Institutional Certification - Before January 25 - Without Consent](#).
- ii. Was this protocol funded after January 25, 2015? Yes No
- If yes, submit the [Extramural Institutional Certification - After January 25](#).

25. Additional Information

In the space below, provide any additional information that you believe may help the IRB review the proposed research, or enter "None." None.

Analysis plan

Planned: We will explore descriptive statistics including means, standard deviations, and confidence intervals for all variables. Aim 1 and Aim 2 are similar from the perspective of data analysis. We will use mixed-factor ANOVA to determine differences in outcomes over time by group. There will be no adjustment for multiple testing of outcomes because the goal of this study is to collect preliminary data. Data collected for feasibility will mostly be descriptive. The data will be summarized for guidance in designing the main trial supported by this pilot study.

Actual: Due to small sample which led to early termination, only descriptive statistics for each group were analyzed.

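### For outcomes measured at weeks 0, 8 and 16, the planned group-by-time test spends one of its two degrees of freedom on weeks 0 to 8, before the arms differ; a week-16 ANCOVA on the pre-diet values is a cheap gain in precision

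*Combined protocol and SAP*

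**What the plan says.** The Analysis plan (Planned) has one sentence on the between-arm comparison: "We will use mixed-factor ANOVA to determine differences in outcomes over time by group". It states no time levels, contrast, covariate or sphericity correction.

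The arms separate late. Under Item 17.a, III Intervention, everyone receives the standard physical activity programme for eight weeks. Then "At the completion of the eighth week, participants will receive their randomization assignment", and "Those in the BIPAMS+Diet arm will begin receiving dietary materials in week 9". The same section describes the first eight weeks as a run-in meant to help isolate the effect of adding diet.

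The measurement schedule divides the outcomes into two sets:

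- **Three visits.** For the symptom questionnaires, "These variables will be measured at baseline, 8 and 16 weeks". The procedures table in Item 17 also lists the accelerometer three times.
- **Two visits.** At week 8, "Participants will not be asked to come into the lab at this point". Bloodwork, anthropometrics, DXA, timed walk, peg test, SDMT and dietary recall are each listed twice. The primary outcome (Item 14.b: lipids, insulin, glucose, anthropometry, DXA) belongs wholly to this set.

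Item 16.e plans 24 participants, 12 per arm. The Analysis plan (Actual) says the trial ended early and only descriptive statistics by group were produced.

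**The concern.** With three visits and two groups, the group-by-time interaction has (3 − 1)(2 − 1) = 2 df. These can be written as a week 0–8 contrast and a contrast of week 16 with the earlier visits. By design the first contains no diet effect. An overall F-test averages the signal over both, so power is lost. A significant F also does not by itself locate the difference in the diet phase, since chance divergence during the run-in adds to it.

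With 12 per arm, precision is the main limit. The week-0 and week-8 values are already scheduled and can serve as covariates at almost no cost. The Analysis plan says the data will guide a main trial, so the choice would matter there if the same test were reused.

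**Working it through.** **Inputs.** From the documents: 12 per arm (Item 16.e), the visit schedule, and no between-arm difference before week 9. The documents give no effect size, SD, correlation, alpha or power, so there is no figure of the plan's own to reproduce. Assumed: unit SD at every visit, two-sided 0.05, an effect of 0.8 SD at week 16 only, and correlation r under two patterns: equal between all visits, or AR(1) with r between adjacent visits.

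**Step 1. Three-visit outcomes: planned test against ANCOVA.** Simulated power (40,000 replicates per cell) of the interaction F on 2 and 44 df, and of week-16 ANCOVA on weeks 0 and 8:

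| r | Equal: ANOVA | Equal: ANCOVA | AR(1): ANOVA | AR(1): ANCOVA |
|---|---|---|---|---|
| 0.3 | 36% | 49% | 33% | 46% |
| 0.5 | 48% | 58% | 42% | 54% |
| 0.7 | 72% | 78% | 59% | 70% |
| 0.8 | 88% | 91% | 76% | 84% |
| 0.9 | 99.5% | 99.5% | 97% | 98% |

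The gain is about 3 to 13 points at r = 0.3 to 0.8 and at most about 2 points at 0.9. Over r = 0.3 to 0.8 it is about 6 to 8 points for an effect of 0.5 SD and about 0.5 to 16 for 1.0 SD.

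Rejection under the null, r = 0.3 to 0.8: ANOVA 5.0–5.8% (4.5–4.9% with the Greenhouse-Geisser correction), ANCOVA 4.8–5.1%.

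Week 8 has to be in the model. ANCOVA on week 0 alone can lose to the planned test: 56% against 59% at AR(1) 0.7, 66% against 76% at AR(1) 0.8, and 86% against 88% at equal correlation 0.8.

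**Step 2. How much of the gain is simply the use of 1 df?** Compare estimator variances, in units of 2σ²/12:

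- Week 16 minus the mean of weeks 0 and 8: 1.5(1 − r) under equal correlation; 1.5 − r/2 − r² under AR(1).
- Week 16 minus week 8: 2(1 − r) under both.
- ANCOVA on both: residual variance times (N − 3)/(N − 5) = 21/19 for two estimated slopes. The residual variance is (1 − r)(1 + 2r)/(1 + r) under equal correlation and 1 − r² under AR(1).

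| Pattern, r | Week 16 − mean(0, 8) | Week 16 − week 8 | ANCOVA on 0 and 8 |
|---|---|---|---|
| Equal 0.3 | 1.05 | 1.40 | 0.95 |
| Equal 0.5 | 0.75 | 1.00 | 0.74 |
| Equal 0.7 | 0.45 | 0.60 | 0.47 |
| Equal 0.8 | 0.30 | 0.40 | 0.32 |
| AR(1) 0.3 | 1.26 | 1.40 | 1.01 |
| AR(1) 0.5 | 1.00 | 1.00 | 0.83 |
| AR(1) 0.7 | 0.66 | 0.60 | 0.56 |
| AR(1) 0.8 | 0.46 | 0.40 | 0.40 |

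Simulated power agrees. Against the mean of weeks 0 and 8, the contrast has 57.7% (ANCOVA 58.2%) at equal correlation 0.5 and 80.0% (78.2%) at 0.7. Against week 8, it has 67.6% (70.2%) at AR(1) 0.7, but about 46% (53%) at AR(1) 0.5.

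**Step 3. Two-visit outcomes, including the primary.** Here the interaction F is the t-test on change from week 0 to week 16, with 1 df. Variances are proportional to 2(1 − r) for change and 1 − r² for ANCOVA, so

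ratio = [(1 + r)/2] × (N − 3)/(N − 4) = [(1 + r)/2] × 21/20.

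| r (weeks 0–16) | 0.3 | 0.5 | 0.7 | 0.8 | 0.9 | 0.95 |
|---|---|---|---|---|---|---|
| ANCOVA/change | 0.683 | 0.788 | 0.893 | 0.945 | 0.998 | 1.024 |

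Break-even: r = 2(20/21) − 1 = 0.905. Mean 95% CI half-width, change against ANCOVA, in SD: 0.84 and 0.74 at r = 0.5; 0.65 and 0.61 at 0.7; 0.53 and 0.52 at 0.8; 0.375 for both at 0.9.

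**Step 4. Is week 8 truly pre-diet?** Assignment is disclosed when week 8 ends, yet "At the half-way point of the intervention (week 8), participants will be asked to wear the accelerometer again for 1 week", and "Accelerometers will be mailed to them and questionnaires will only be done online". The documents do not fix the order. If week-8 data followed disclosure and already carried an assumed 0.1 SD of response, ANCOVA would understate the effect by 0.1 times the week-8 slope. For r = 0.5 to 0.8 the slope is r/(1 + r) = 0.33 to 0.44 (equal) or r = 0.5 to 0.8 (AR(1)), giving about 0.03 to 0.08 SD.

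**The case against.** The case for leaving the plan alone is fair in several respects.

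- **It is not an error.** The planned test is unbiased with type I error close to nominal, in a 24-person pilot, and it was never run. That stands, and it limits the point to an improvement.
- **The primary outcomes are not affected in this way.** A reader might infer that the whole ANOVA wastes a degree of freedom on the run-in. The schedule does not support that: outcomes with two visits have a 1-df test. It spans weeks 0 to 16 but spends nothing separately on weeks 0 to 8. The loss of a degree of freedom falls on the secondary symptom measures and on accelerometry, which Item 14.b does not list as an outcome.
- **Naming a contrast would do.** This is partly right. The plan does not exclude a contrast, and under equal correlation of about 0.5 or more, week 16 against the mean of the earlier visits matches or slightly beats ANCOVA. But Step 2 shows that the better contrast changes with the correlation pattern, which is unknown, while ANCOVA on both values is best or close to best in every row.
- **The size is assumed.** It is. Equal variance across visits is also doubtful for accelerometry, whose wear period differs between sections.

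**Conclusion.** The point holds as a minor matter of efficiency. For questionnaires and accelerometry, the planned 2-df test gives up about 3 to 13 power points against ANCOVA on weeks 0 and 8, assuming 12 per arm, 0.8 SD and correlations of 0.3 to 0.8. Part of that is recoverable with a named contrast, and almost none remains at 0.9. For two-visit outcomes, including the primary, the planned test is valid and ANCOVA is usually but not always more precise: variance 32% to 5% lower at 0.3 to 0.8, about equal at 0.905, and 2% higher at 0.95. If weight, BMI or DXA values correlate at 0.9 or above (an assumption), they gain nothing.

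A reader might also infer that the trial's reported findings are in doubt. They are not, on this ground: only descriptive statistics were analysed. Nor do the documents say that the main trial would reuse this test, so the benefit there is conditional.

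**What to change.** Replace the ANOVA sentence with:

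> For each outcome measured at baseline and week 16, the between-arm difference at week 16 will be estimated by ANCOVA with its 95% CI, adjusted for the week-0 and week-8 values where both are collected (questionnaires, accelerometry) and for the week-0 value otherwise (labs, anthropometry, DXA, timed walk, peg test, SDMT, dietary recall).

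Add:

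> Week-8 questionnaires and accelerometer wear will be completed before the assignment is disclosed.

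A pre-specified 1-df contrast is an acceptable smaller change, but it requires choosing a contrast without knowing the correlation pattern.

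Two passages need reconciling first:

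- **EDSS.** The procedures table lists it once, while Item 17.a, IV says "All baseline testing will be repeated following the same protocols as baseline". It can enter this analysis only if it is repeated.
- **Accelerometer wear.** It is 14 days in the baseline section, one week at week 8, and 7 days in the procedures table.

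Cost: one or two df for covariates already scheduled, and accelerometer wear must finish by the end of week 8. There is no gain where the correlation is about 0.9 or more. ANCOVA needs the same complete visits as the ANOVA, so it neither helps nor harms on missing data. It also cannot separate run-in change from diet-phase change for outcomes without a week-8 value. If the main trial would reuse the planned test, make the same change there.
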